#### Medications and Therapies:

Concomitant medications/therapies are any events with administration dates and times on or after the date and time of the first study drug dose. If the start date of a medication or therapy is partially or completely missing and the end (stop) date and time of the medication/therapy does not indicate that it occurred prior to first dose, then the determination of concomitant status will be based on the following:

If the start year is after the year of the first study drug dose, then the medication/therapy is concomitant; else,

If the start year is the same as the year of the first study drug dose and the start month is missing, then the medication/therapy is concomitant; else if the start month is present and is the same or after the month of the first study drug dose, then the medication/therapy is concomitant; else, if the start date is completely missing, then the medication/therapy is concomitant.

All other medications/therapies are considered prior medications/therapies and could occur from the 30 days prior to informed consent up through the Run-In Period and prior to the 1st dose.

Normal Reference ranges for PPi and PLP:

PPi (μM):	
Male/Female	
13-18 years 0.75-4.78	
>18 years 1-5.82	

PLP (ng/mL):
Male/Female
6-18 years 5.74-61.15
>18 years 2.81-26.70

For observations that fall under the lower limit of quantification (LLOQ), the following values will be used:

Table 4:	Values	Used for	Observat	tions under	the Lower	Limit o	of Q	uantification	(LLOC	))
----------	--------	----------	----------	-------------	-----------	---------	------	---------------	-------	----

Parameter	Value Used
Plasma PPi	0.75µM
Plasma PLP	2.5ng/mL
Serum PTH	.5 x LLOQ

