#### 7.1.4. Prior and Concomitant Medications / Therapies

Concomitant medication/therapy data and prior- medication data will be presented in by-patient data listings. See Appendix 9.1 for additional details on the definition of prior and concomitant medications/therapies and rules for handling missing or incomplete start and stop dates. Concomitant medications and therapies will also be summarized in tabular form by anatomic class (ATC) level 3 and generic name for the FA Set by treatment cohort and overall using frequencies and percentages. The WHO Drug dictionary (DD) version from MAR2015 or later will be used to code the medications.

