#### 7.2.2. Secondary Endpoint

For the secondary endpoint, PLP change from Baseline to pre-3rd dose Week 9, similar methods as for PPi will be employed in the FA Set and PP Set.

Sensitivity analyses for PLP may be employed for any patients without taking any vitamin B6 or with consistent input of vitamin B6, defined as taking same dose of vitamin B6 during the study. Vitamin B6 usage will be obtained from the concomitant medications.

Additionally for sensitivity, the within-patient mean absolute levels of the pre-treatment "fasting" PLP samples (-168 h, -24 h, pre-dose Day 1) and the "non-fasting" PLP samples (-156 h, -12 h) will be compared using the exact Wilcoxon rank-sum test for all patients in the FA Set. If a statistical difference is detected between the pre-treatment "fasting" and "non-fasting" samples, given samples on treatment are collected under both "fasting" and "non-fasting"

conditions, the change to each post-treatment timepoint will be evaluated descriptively using the matched "fasting" or "non-fasting" average at Baseline; accordingly, "fasting" post-treatment samples will use a "fasting" Baseline and "non-fasting" post-treatment samples will use a "non-fasting" Baseline.

Please refer to Table 4 on how to handle the values fall under the lower limit of quantification (LLOQ).

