#### **Adverse Events**

Additional details for the analysis of Adverse Events described in Section 7.3.2:

Treatment-emergent AEs (TEAEs) are events with start dates and start times on or after the date and time of the first study drug dose. If the start date of an AE is partially or completely missing and the end (stop) date and time of the AE does not indicate that it occurred prior to first dose, then the determination of treatment-emergent status will be based on the following:

If the start year is after the year of the first study drug dose, then the AE is treatment-emergent; else,

If the start year is the same as the year of the first study drug dose and the start month is missing, then the AE is treatment emergent; else if the start month is present and is the same or after the month of the first study drug dose, then the AE is treatment-emergent; else, if the start date is completely missing, then the AE is treatment-emergent.

Pre-Treatment Adverse Events (PTAEs) are the AEs occur after the time of informed consent up through the Run-In Period and prior to the 1st dose.

Patient percentages are based on the total number of treated patients in the particular treatment cohort.

Related AEs are defined as possible, probable or definitely related, or events with missing relationship status. Unrelated AEs are defined as unlikely or not related.

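### SAP Appendix 9.3 decides concomitant status from the start date alone when that date is partial, so a drug still taken on study can be classed as prior (minor, but wrong as written)

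*SAP*

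**What the plan says.** The rule is under Medications and Therapies in SAP Appendix 9.3, and it has three parts.

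- **General definition.** "Concomitant medications/therapies are any events with administration dates and times on or after the date and time of the first study drug dose". The criterion is administration during treatment, not when the drug was begun.
- **Incomplete start dates.** If the start date is partly or wholly missing and the stop date does not show that use ended before first dose, "then the determination of concomitant status will be based on the following". The branches that follow test the start year, the start month, or a wholly missing start. The last one reads: "else, if the start date is completely missing, then the medication/therapy is concomitant".
- **Residual class.** "All other medications/therapies are considered prior medications/therapies and could occur from the 30 days prior to informed consent up through the Run-In Period". The sentence ends by placing these drugs before the first dose.

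The branches match the treatment-emergence rule given just above under Adverse Events, for example: "If the start year is after the year of the first study drug dose, then the AE is treatment-emergent; else".

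The classification is used in SAP 7.1.4, where all medication data are listed but only one class is tabulated: "Concomitant medications and therapies will also be summarized in tabular form". It may also be used in SAP 7.2.2, which says of an optional PLP sensitivity analysis: "Vitamin B6 usage will be obtained from the concomitant medications".

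**The concern.** Onset is the right criterion for a treatment-emergent adverse event. For concomitant medication the criterion is overlap with treatment, as the section's own first sentence says. In the incomplete-date rule the stop date only screens out drugs that ended before first dose. No branch makes a drug concomitant because it is ongoing or was stopped after first dose. A long-standing drug whose start is known only to the month or year can therefore fall into the residual class while the patient is still taking it.

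Old, partly known start dates are foreseeable. The schedule footnotes (Protocol Table 2 footnote 9, SAP Table 2 footnote 8) call for historical use of HPP-related medication. Protocol 7.1 waives the PLP criterion for patients on pyridoxine, so vitamin B6 use begun before first dose is expected.

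What is at stake is the completeness of one descriptive table and, on one reading of SAP 7.2.2, membership of one optional sensitivity set for the secondary endpoint.

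**Working it through.** No planned figure bears on this point, so the check traces the rule as written.

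**Inputs.** The rule is from SAP Appendix 9.3. First dose is assumed to be Monday 6 June 2016: the protocol requires a Monday, and Administrative Change Letter #2 moves the estimated first enrolment to Q2 2016. The drug is assumed to be ongoing, so every record passes the stop-date screen.

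**Rule.** Let Y and M be the recorded start year and month, and Y0 = 2016 and M0 = 6 those of first dose. A record is concomitant if:

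1. Y > Y0; or
2. Y = Y0 and M is missing; or
3. M is present and M ≥ M0; or
4. the start is wholly missing.

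Otherwise it is prior. Branch 3 states no year of its own. Nested reading: it applies only when Y = Y0. Un-nested reading: it applies for any Y.

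| Recorded start (drug ongoing) | Nested | Un-nested | Stop-date rule |
|---|---|---|---|
| 2012, month unknown | prior | prior | concomitant |
| Mar 2014 | prior | prior | concomitant |
| Sep 2014 | prior | concomitant | concomitant |
| Feb 2016 | prior | prior | concomitant |
| 2016, month unknown | concomitant | concomitant | concomitant |
| Jun 2016 | concomitant | concomitant | concomitant |
| Jul 2016 | concomitant | concomitant | concomitant |
| wholly missing | concomitant | concomitant | concomitant |

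Four of the eight records are prior on the nested reading and three of eight on the un-nested reading. None should be, since none stopped before first dose. These are constructed cases, and the counts do not estimate a rate in the trial.

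**Comparison within one drug.** An ongoing drug with start 15 Mar 2010 has a complete date, so the general definition alone governs and it is concomitant. With start Mar 2010 (2010 < 2016 and 3 < 6) it meets no branch on either reading and is prior. With no start date at all it meets branch 4 and is concomitant. Partial knowledge thus gives a different class from both full knowledge and none.

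**Other stop states.**

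- A stop on 20 July 2016 gives the same results as ongoing use.
- With no stop date and no ongoing flag, start 2010 is prior and a wholly missing start is concomitant.
- A stop in April 2016, before first dose, gives prior under both the written rule and the stop-date rule.

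**Consistency with the closing sentence.** That sentence places prior drugs before the first dose. An ongoing drug sent there by default does not fit the description, so the section contradicts itself at both ends.

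**Vitamin B6.** Suppose SAP 7.2.2 means the derived class. A patient whose vitamin B6 start is recorded as 2012 and who stops on study has that record classed as prior. The patient then looks like a non-user and is kept in the set. A stable-dose user belongs in the set either way.

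**The case against.** The best counter-argument is that the section can be read coherently. The first sentence makes any on-study administration concomitant, the last describes prior drugs as occurring before first dose, and fallback rules for incomplete dates normally serve records whose status is otherwise unknown. A sensible programmer could let the first sentence govern. That is a fair account of the likely intent, but the text expressly sends these records to the branches and gives ongoing use no precedence. Two programmers could differ, and the literal one would be following the SAP.

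A reader might also infer that every partial start date in an earlier year makes an ongoing drug prior. The text does not support that. Because the month clause has no year condition of its own, Sep 2014 is prior on one reading and concomitant on the other. This is a second ambiguity, and it limits the firm claim to the three start patterns named in the verdict.

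The vitamin B6 consequence depends on several conditions at once: a user with a partial earlier start, a stop on study, an analysis that is only optional, and the derived-class reading of SAP 7.2.2. The schedule footnotes use the term concomitant medications for everything collected from 30 days before entry, which favours the broader reading. A dose change is less certain still. If it is entered as a new line with an on-study start, that line is concomitant and shows use beginning mid-study, so the patient would not pass as a constant-dose user. The documents do not show how changes are recorded.

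Finally, the sensitivity analysis in SAP 7.2.1.5 for medications that might affect PPi refers to any medications given, so it is not tied to this class.

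**Conclusion.** The point holds as a minor error in a stated rule. For a drug still taken on study, the written rule gives prior when the start is an earlier year with no month, an earlier year with a month before the first-dose month, or an earlier month of the first-dose year. An earlier year with the same or a later month is ambiguous. This rests on reading the branches as binding for the records that the SAP sends to them.

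The reach is one descriptive table, with the listings intact. The optional PLP sensitivity set is reached only if SAP 7.2.2 means the derived class, and then firmly only for a vitamin B6 user who stops on study.

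A reader might infer that the PLP secondary analysis or the PPi result is biased. The documents do not support this: neither the primary repeated-measures model nor the ANCOVA uses the classification, and the only PLP analysis exposed is the optional one. The number of records or patients affected cannot be derived.

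**What to change.** In SAP Appendix 9.3, replace the start-date branches for medications with:

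*A medication/therapy is concomitant if it started on or after first dose, is ongoing, or has a stop date on or after first dose, or if the available stop-date parts do not rule this out, whatever its start date; it is prior only if it stopped before first dose. Records with an unknown stop date and no ongoing flag are concomitant by convention.*

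This brings partial dates into line with the section's own definition and with its treatment of wholly missing starts. It also removes the month-clause ambiguity.

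In SAP 7.2.2, state that vitamin B6 use and dose constancy are taken from all medication records overlapping the study period.

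The cost is two sentences, one clause and one derivation, with no new data. The downside comes from the capture of historical HPP-related medication in the schedule footnotes: some long-past drugs with no recorded stop may enter the concomitant table. They can be flagged there. SAP 4.1 and Administrative Change Letter #2 restate a 30-day collection window, so how many such records would exist is unclear.

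Editorial only: SAP 7.1.4 says "See Appendix 9.1 for additional details on the definition of prior and concomitant medications/therapies", but the definitions are in Appendix 9.3, and the reference should be corrected.
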